#### 3.2.2 Exclusion Criteria

Individual patients may only be allowed to drink clear fluids up to call to operating room if they fulfill none of the following criteria:

- 1. Absolute indication for rapid sequence induction including but not limited to:
  - a. Bowel obstruction including ileus
  - b. Stricture and oesophageal disorders including achalasia
  - c. Recent polytrauma or trauma of the upper gastrointestinal tract
  - d. Acute abdomen/peritonitis including active gastrointestinal bleeding
- 2. Relative indication for (modified) rapid sequence induction includes, but is not limited to:
  - a. Symptomatic gastroesophageal reflux disease, independent of food intake and persistent under medical treatment (PPI)
  - b. Hiatus hernia or upside down stomach
  - c. Upper gastrointestinal tumour
  - d. History of upper gastrointestinal surgery (oesophageal, gastric, duodenum, pancreatic)
  - e. Medically confirmed gastroparesis
  - f. Severe obesity, defined as body mass index ≥ 40 kg/m^2
- 3. Dysphagia
- 4. Renal replacement therapy
- 5. Fluid restriction therapy
- 6. Pregnancy
- 7. Expected need for postoperative mechanical ventilation
- 8. Prior enrolment in this trial.

## 3.3 Adherence

## 3.3.1 Compliance

Physicians will retain the right to assign patients to a fasting regime as per national guideline and/or postpone anaesthesia induction if they are concerned for patient safety due to unforeseen risk factors for bronchopulmonary aspiration.

## 3.4 Concomitant Care

As shown by Rüggeberg et al., allowing patients fluid intake until call to the operating room on its own does not reduce fasting times. Only if it is combined with encouraging the patients to drink the fasting time decreases signifficantly. We therefore estimate the effects of contamination bias to be small. To reduce the risk of timing bias the day-of-surgery-visit of the study staff to reencourage drinking is aimed to take place 2 h before anaesthesia is scheduled.

#### 3.4.1 Overdose and Abuse

To ensure minimal risk of bronchopulmonary aspiration the attending anaesthesiologist retains the right to postpone anaesthesia induction, which is warranted in cases, where the patient exceeds the 200 ml fluids intake in the last 2 h or has consumed solid foods less than 6 h before anaesthesia induction.

## 3.5 Outcomes

# 3.5.1 Primary Outcome

The primary efficacy outcome is adapted from item #3 of the Bauer satisfaction questionnaire and measured prior to anaesthesia induction of anaesthesia: Have you had the following today: Thirst (No/ Yes, moderate/ Yes, severe)

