# 1.2 Synopsis

Title	A pilot study to test benefits of drinking clear fluids until called to the operating room in adult surgical patients.		
Short title	HYDRATE-Study		
Indication	Patients ≥ 18 years of age undergoing surgery without an indication for rapid sequence induction.		
Primary end point	
 
Primary efficacy endpoint:
 
Patient thirst (No; Yes, moderate; Yes, severe)
 
Endpoint will be measured prior to anaesthesia induction.
 
		
Secondary end points	Endpoint will be measured prior to anaesthesia induction.  Key secondary endpoints:  We will pilot test the intervention to demonstrate its acceptability and feasibility and to identify target outcomes for further trials.  Piloting for feasibility assessment:  Total number of protocol deviations per group  Outcome assessment successfully blinded  Real fluid fasting time is less than allocated fluid fasting time  Fluid fasting time		

	Piloting for future power calculations: Richmond Agitation Sedation Scale (RASS) Confusion Assessment Method for the Intensive Care Unit (CAM-ICU) Headache Vital signs (delta heart rate, delta blood pressure) Cumulative Vasopressor dose within 15 min after anaesthesia induction Blood glucose level Number of attempts for placing a peripheral intravenous catheter Postoperative nausea and vomiting (PONV)  Safety Endpoints: Unplanned intensive/intermediate care unit stay due to respiratory complications
	

Confirmed bronchopulmonary aspiration

Death within observation period

Trial design	The study is a prospective, single centre, outcome assessor
Trial population	blinded, controlled randomised clinical trial (RCT) with 3 arms.  Inclusion criteria on the individual level: Patients ≥ 18 years of age scheduled for surgery under anaesthesia care (general anaesthesia, regional anaesthesia, combined anaesthesia or monitored anaesthesia care) with an ASA physical status classification I-III.  Exclusion criteria: Absolute and relative indication for rapid sequence induction, dysphagia, renal replacement therapy, fluid restriction therapy, pregnancy, expected need for postoperative mechanical ventilation and prior enrolment in this trial.
Sample size	n = 174 (55 per group +5% drop-outs = 58 per group)

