## 3.6.3 Visit 3: Assessments prior to anaesthesia induction

To ensure safety, 30 min must have passed since call to the operation room and anaesthesia induction. The patient must also state that they have not drunk since being called to the operating room.

Anaesthesia induction in the sense of this protocol is defined as the beginning of the injection of the hypnotic for general anaesthesia and beginning of the injection of the local anaesthetic for local/regional anaesthesia.

- The primary efficacy outcome is measured immediately before anaesthesia induction of anaesthesia. Authorised medical staff use a modified Bauer satisfaction questionnaire to assess thirst.
- To assess secondary outcomes the questionnaire will include an item for headache.
- To assure the number of attempts for placing a peripheral intravenous catheter is documented correctly, each staff member involved in the anaesthesia of the patient is interviewed.
- Vital signs including heart rate and blood pressure will be collected from the routine data. The highest value 5 min prior to anaesthesia induction of anaesthesia will be documented.

• The blood sample for glucose levels might be drawn immediately prior to anaesthesia induction or immediately after anaesthesia induction (Values assessed within 15 min prior and 15 min after anaesthesia induction will be accepted).

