## 5.4.1 Statistical Hypotheses/Statistical Estimation Method

H0: Clear fluid intake until call to the operating room is not associated with reduced thirst at anaesthesia induction compared to restriction of clear fluid intake within 2 hours prior to anaesthesia induction on the Bauer satsifaction questionnaire item #3.

The primary endpoint will be analysed by chi-square test.

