# 5.5 Sample Size

We plan randomising n=174 patients. n = 174 (55 per group +5% Dropout)

The primary endpoint of this study is thirst immediately before anaesthesia induction. For this purpose, the Bauer Satisfaction Questionnaire is dichotomised - "yes (moderate or strong)" vs. "no thirst". The three groups will be compared with each other. In the control group, based on Bauer et al, 2001, a value of 53% is assumed based on our own experience it is assumed that the experimental intervention (group 3) has a relative effect of 50% and therefore only 26.5% of patients are still thirsty. For group 2 (Instructed guideline adherence) a somewhat weaker effect is assumed. We assume that thirst can be reduced to 30% in this group.

In order to detect these differences between all three groups using a Chi² test with a power of 80%, a total of 165 patients is needed - 55 patients per group.

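### The primary item as printed asks about thirst over the day, H0 concerns thirst at induction, and the protocol does not reconcile the two

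*Combined protocol and SAP*

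**What the plan says.** Section 3.5.1 describes the primary outcome as "adapted from item #3 of the Bauer satisfaction questionnaire" and prints it as "Have you had the following today: Thirst (No/ Yes, moderate/ Yes, severe". No other wording of the item appears in the protocol.

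Section 5.4.1 states the null hypothesis that drinking until the call "is not associated with reduced thirst at anaesthesia induction", compared with restriction in the last 2 hours, and specifies that this is assessed "on the Bauer satsifaction questionnaire item #3".

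Section 5.5 says: "The primary endpoint of this study is thirst immediately before anaesthesia induction". It then dichotomises the answer, so that either grade of yes counts as thirsty. The assumed rates are 53% (usual care, taken from the cited 2001 questionnaire study), 30% (Group 2) and 26.5% (Group 3).

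On timing, the Synopsis says "Endpoint will be measured prior to anaesthesia induction". Section 3.6.3 places the assessment directly before induction and adds: "Authorised medical staff use a modified Bauer satisfaction questionnaire to assess thirst". The hypothesis (Section 2.2.1) and the primary objective (Section 2.3.1) speak of reducing or improving thirst and attach no time point to the thirst itself.

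**The concern.** A time of asking and a recall period are different things. The protocol fixes the first consistently, but for the second it gives two answers: the printed item covers the day so far, while H0 covers the moment of induction.

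The difference matters for this intervention. Under Section 3.2, Group 3's instructions differ from Group 2's only from 2 h before induction until the call. If a drink in that window relieves thirst already felt, the state named in H0 has improved, yet the truthful answer to the printed question is still yes. A difference between arms, or the lack of one, could then be reported as a finding about thirst at induction when the data do not isolate that state. It could not be repaired afterwards, because a recorded yes to the day-long question cannot later be split into current and earlier thirst.

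**Working it through.** **Step 1. Set the sections side by side.**

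| Section | What it fixes | Time reference |
|---|---|---|
| 3.5.1 (printed item) | Period the answer covers | The day so far |
| 5.4.1 (H0) | State to be compared, using the same item | At induction |
| 5.5 (sample size) | Endpoint label | Just before induction; could be the state or only the time of measurement |
| 1.2 and 3.6.3 | When the question is asked | Before, or directly before, induction |
| 2.2.1 and 2.3.1 | Hypothesis and objective | None attached to thirst |

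The firm conflict is between 3.5.1 and 5.4.1. Section 5.5 adds to it on one reading only.

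**Step 2. Follow the three kinds of patient through the printed item and the dichotomy in Section 5.5.**

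| Patient | Truthful answer | Counted as | State named in H0 |
|---|---|---|---|
| Thirsty at induction | Yes | Thirsty | Present |
| Thirsty earlier, relieved by induction | Yes | Thirsty | Absent |
| Not thirsty at any time that day | No | Not thirsty | Absent |

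The middle row is where the item and H0 part company. The item does capture thirst at induction, but merges it with earlier thirst.

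**Step 3. Check whether the planned sample size is at fault.** Inputs from Section 5.5: rates 0.53, 0.30 and 0.265; 55 evaluable per group, N = 165; three-group chi-square test, 2 degrees of freedom. Alpha = 0.05 comes from the Synopsis.

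- Mean rate: (0.53 + 0.30 + 0.265)/3 = 0.365.
- Effect size: w² = mean squared deviation / [0.365 × (1 − 0.365)] = [(0.165² + 0.065² + 0.100²)/3] / 0.2318 = 0.01382/0.2318 = 0.0596.
- Noncentrality: N × w² = 165 × 0.0596 = 9.84.
- Power from the noncentral chi-square: 80.9% (simulation with 200,000 trials: 80.8%). The smallest N giving 80% is 162, so the stated 165 reproduces.
- Dropout: 55/0.95 = 57.9, rounded up to 58 per group; 3 × 58 = 174, as stated.

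The arithmetic is sound for whatever period the three rates describe.

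**Step 4. Ask which period that is.** Section 5.5 does not say. If the rates describe the item as printed, planned power stays at 81%. If they describe thirst at induction, the rates on the printed item would depend on how many patients in each arm were thirsty earlier and then relieved. The documents give no figure for that in any arm, so neither the size nor the direction of an effect on power can be derived.

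**The case against.** The strongest defence is that the endpoint can be run as written. Instrument, answer scale and time of asking agree across sections. Section 5.5's phrase reads naturally as the time of measurement. All arms get the same question at the same point, from assessors planned to be blinded. The hypothesis and objective do not confine thirst to induction, and Groups 2 and 3 are both encouraged to drink before the 2 h mark, so thirst over the day is a legitimate target. The item is described as adapted and the questionnaire as modified, so the form patients see may already ask about the present.

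Most of this stands, and it limits the point. It does not remove the mismatch between the printed item and H0, because nothing in the protocol says that the day-long wording means current thirst.

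Three stronger inferences are tempting and should be resisted:

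- **That the trial is underpowered because earlier thirst dilutes the contrast.** This needs rates of earlier, relieved thirst by arm, which the documents do not contain. The 53% is drawn from a study of the questionnaire itself, so it may well belong to the item as printed.
- **That Section 5.5 independently commits the trial to a present state** because it says "therefore only 26.5% of patients are still thirsty". In context this can simply mean the share left after the assumed 50% reduction.
- **That the comparison between arms is biased.** It is not shown to be. It remains a valid randomised comparison of what the item measures.

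**Conclusion.** The mismatch between Sections 3.5.1 and 5.4.1 is certain on the text, and it bears on the primary endpoint. As printed, the trial compares any thirst on the day of surgery up to the time of asking, while H0 asks about thirst at induction. The consequence is one of interpretation: a result on the printed item does not by itself support or refute H0.

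The numerical consequence is not established. Planned omnibus power is 81% at 55 per group if the assumed rates refer to the item as printed, and no other figure can be derived from the documents.

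The conclusion rests on the plain reading of the printed question and concerns the protocol text only, since the patient form and assessor instructions are not included. It should be fixed before enrolment because it is cheap then and cannot be corrected from the data later.

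**What to change.** Before the first patient is enrolled, make Sections 3.5.1, 5.4.1 and 5.5 agree on one period, and state in Section 5.5 which period the 53% control rate is assumed to cover.

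If the patient form or the assessor instructions already ask about the present, print that wording in Section 3.5.1. That is a text change only.

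Otherwise choose one of the following:

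- **(a) Add a current-thirst question at Visit 3** with the same three answers, make it the measure of H0, and keep the day-long item beside it. The Visit 5 questionnaire cannot stand in for the day-long item, because by then the day includes postoperative thirst. Cost: one more line on the Visit 3 questionnaire and in the eCRF, and a looser link to the cited basis for the 53%.
- **(b) Keep the day-long item as primary** and restate the endpoint and H0 as any thirst on the day of surgery up to induction, with the three planning rates stated for that period. Cost: text changes only, but the trial then does not test thirst at induction.

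Either option touches the primary endpoint, so ethics reappraisal under Section 7.3 may be needed if the protocol has already been appraised.

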## 3.5.2 Secondary Outcome

#### Piloting for feasibility assessment:

- 1. Total number of protocol deviations per group
  - a. Outcome assessment successfully blinded
  - b. Violation of fluid fasting time and fluid fasting time in general

## Piloting for future power calculations:

- 2. Richmond Agitation Sedation Scale (RASS)
- Confusion Assessment Method for the Intensive Care Unit (CAM-ICU)
- 4. Headache
- 5. Vital signs (delta HF, delta RR)
- 6. Cumulative vasopressor dose within 15 min after anaesthesia induction
- 7. Blood alucose level
- 8. Number of attempts for placing a peripheral intravenous catheter
- 9. Postoperative nausea and vomiting (PONV)

## Safety Endpoints:

- 10. Unplanned postoperative admission to an intermediate care unit (IMC) or intensive care unit (ICU) due to respiratory insufficiency.
- 11. Confirmed Bronchopulmonary aspiration
- 12. Death within observation period

## 3.5.3 Analysed population

See inclusion and exclusion criteria. Analysis is per intention to treat.

# 3.6 Participant Timeline and Individual Study Visits

Follow-up per patient: Until completion of the last Visit (regularly 2 h ± 30 min after procedure, up to 48 h after procedure if e.g. bronchopulmonary aspiration is suspected.)

Duration of intervention per patient: From randomisation until call to the operating room.

Informed Consent, inclusion and withdrawal from the study is handled according to ICH-GCP.

## 3.6.1 Visit 1: Enrolment in the Trial

## Screening, registration and Randomisation (- 28 days up to -0 days before surgery):

Generally, the investigator or authorised qualified members of the study group in the trial site screen potential patients eligible for recruitment up to 28 days before surgery for general participation on the basis of pre-existing data (e.g., as available in medical records).

Registered patients will be randomised electronically using REDCap after enrolment: Qualified medical staff will gain limited access to the system using a personal password. Information to identify a participant uniquely and to confirm eligibility must be entered before the system will assign the randomised treatment allocation. Randomization will be automated by computer-assisted generation of random numbers, which will be transferred into a randomization decision and triggered web-based by qualified medical staff, so that allocation to the interventions is ensured (allocation concealment).

On the day of the surgery the patients fluid intake prior to anaesthesia will be noted on a worksheet. The respective worksheet will be handed out at enrolment to avoid recall bias. However, if the patient loses the worksheet, a new one is given to him. To ensure outcome assessor blinding the worksheet will be sealed in an envelope after the call to the operation room and until follow up is concluded.

## 3.6.2 Visit 2: Intervention

The intervention is described in detail in chapter 3.2.

## 3.6.3 Visit 3: Assessments prior to anaesthesia induction

To ensure safety, 30 min must have passed since call to the operation room and anaesthesia induction. The patient must also state that they have not drunk since being called to the operating room.

Anaesthesia induction in the sense of this protocol is defined as the beginning of the injection of the hypnotic for general anaesthesia and beginning of the injection of the local anaesthetic for local/regional anaesthesia.

- The primary efficacy outcome is measured immediately before anaesthesia induction of anaesthesia. Authorised medical staff use a modified Bauer satisfaction questionnaire to assess thirst.
- To assess secondary outcomes the questionnaire will include an item for headache.
- To assure the number of attempts for placing a peripheral intravenous catheter is documented correctly, each staff member involved in the anaesthesia of the patient is interviewed.
- Vital signs including heart rate and blood pressure will be collected from the routine data. The highest value 5 min prior to anaesthesia induction of anaesthesia will be documented.

• The blood sample for glucose levels might be drawn immediately prior to anaesthesia induction or immediately after anaesthesia induction (Values assessed within 15 min prior and 15 min after anaesthesia induction will be accepted).

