## 2.1.1 Dehydration

Contradicting to "primum non nocere" the current practise may harm patients due to dehydration. Dehydration has been shown to worsen the outcome of strokes , raises the risk of infection, may prolong length of stay, lead to thrombosis, ACS or acute kidney injury. Dehydration aggravates pain in general and is discussed as a risk factor for post-lumbar puncture headache from iatrogenic spinal fluid leak .

Parenteral hydration may be considered as a solution, but the risk of infection increases with the time after IV-catheter insertion. Besides the typical risks and complications of an IV-catheter it also reduces patient mobility and contributes to patient stress. This contradicts modern treatment principles like Fast-Track. Furthermore, parenteral hydration does not alleviate dry mouth.

The first principle of 2017 NICE (National Institute of Health and Care Excellence) Recommendations is "Provide intravenous (IV) fluid therapy only for patients whose needs cannot be met by oral or enteral routes [...]". NICE further argues that a significant number of hospitalised patients were dying as a result of infusion of too much or too little fluid. 

According to NICE warning signs for dehydration include but are not limited to:

- systolic blood pressure is less than 100 mmHg
- heart rate is more than 90 beats per minute

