## 2.2.2 Risk-Benefit Considerations

Besides the change in preoperative fluid intake, all patients will receive standard perioperative care.

Taking the available data into account it is unlikely for patients in the intervention group to have a substantially higher risk of bronchopulmonary aspiration or a different severity of bronchopulmonary aspiration complications.

Instead, they will be much less likely to experience excessive preoperative fasting durations, which may lead to preoperative dehydration and subsequently contribute to hypotension after anaesthesia induction. This will furthermore improve patient discomfort characterized by increased hunger, thirst, anxiety, sadness, pain, stress and nausea and may even positively influence early postoperative delirium^11 as well as the length of the hospital stay.

In paediatrics and labouring women as well as for adults  allowing clear fluid intake until call to the operating room was already successfully implemented without an increase in bronchopulmonary aspirations being reported.

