## 3.6.4 Visit 4: Assessments immediately after anaesthesia induction

- If relevant bronchopulmonary aspiration is suspected, it needs to be confirmed by bronchoscopy or radiology imaging up to 48 h after anaesthesia procedure. In that case the patient will be monitored for an additional 48 h and the outcome will be documented in the eCRF and the AE/SAE section if applicable. The sponsor is to be informed of every instance of confirmed bronchopulmonary aspiration within 24 h even if the SAE criteria are not met. The risk/benefit consideration has to be revaluated.
- Vital signs including heart rate and blood pressure will be collected from the routine data. The lowest value 15 min after anaesthesia induction will be documented.
- If not already done, a blood sample for glucose levels is to be drawn.

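### The blood-pressure and heart-rate delta is undefined; from the values recorded it overstates the fall, and it cannot show a drinking effect already present before induction

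*Combined protocol and SAP*

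**What the plan says.** The synopsis (Section 1.2) names the outcome as "Vital signs (delta heart rate, delta blood pressure"). Section 3.5.2, under piloting for future power calculations, has "Vital signs (delta HF, delta RR"). Neither place gives a formula.

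The values to be recorded are in the visit descriptions:

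- Section 3.6.3 (Visit 3, before induction): "The highest value 5 min prior to anaesthesia induction of anaesthesia will be documented".
- Section 3.6.4 (Visit 4, after induction): "The lowest value 15 min after anaesthesia induction will be documented".

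On the source, Section 3.6.3 says: "Vital signs including heart rate and blood pressure will be collected from the routine data"; Section 3.6.4 says the same. The number and spacing of readings are not fixed.

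On timing, Section 3.6 gives the duration of the intervention as "From randomisation until call to the operating room". Section 3.6.3 requires 30 minutes between that call and induction.

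On what drinking might change, Section 2.2.2 says that preoperative dehydration may "subsequently contribute to hypotension after anaesthesia induction". Section 2.1.1 lists as warning signs of dehydration that "systolic blood pressure is less than 100 mmHg" and a heart rate above 90 beats per minute.

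**The concern.** Section 2.3.2 says the secondary outcomes should identify targets for further trials, and this one is collected to inform later power calculations. It should therefore give a usable mean and SD and be able to show the effect the protocol expects.

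Two features work against that, and they are independent of each other. Taking the highest value on one side and the lowest on the other produces a fall from ordinary variation, and its size depends on how often routine monitoring takes a reading. Separately, the value that serves as baseline is measured after patients have drunk or fasted as allocated. If drinking has already changed blood pressure or heart rate by then, subtracting that value removes part or all of the effect.

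**Working it through.** **Inputs.** From the documents: highest value in the 5 minutes before induction, lowest in the 15 minutes after, intervention ending at the call to the operating room. Not in the documents, so assumed: within-patient SD 8 units (range 3 to 10), 1 to 5 readings before and 3 to 15 after induction, lag-1 correlation 0 or 0.8, and drinking effects of 0 to 5 mmHg.

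**The plan's own figure.** The documents give no figure for the delta. The only sample-size calculation is for thirst. A three-group chi-square test (2 df, alpha 0.05) with rates of 53%, 30% and 26.5% gives 80.9% power at 55 per group, and 55/0.95 = 57.9, so 58 per group. That reproduces the plan and does not involve the delta.

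**Step 1: the only available delta.** One value is recorded on each side, so delta = max(pre) − min(post).

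**Step 2: built-in fall with no true change.** For independent normal readings, E[delta] = SD × (c_a + c_b), where c_k is the expected maximum of k standard normal readings: c_1 = 0, c_2 = 0.561, c_3 = 0.846, c_5 = 1.163, c_6 = 1.268, c_15 = 1.736.

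| Readings pre/post | c_a + c_b | Fall at SD 8, independent | Fall at SD 8, lag-1 correlation 0.8 |
|---|---|---|---|
| 1/3 | 0.85 | 6.8 | 0.42 × 8 = 3.4 |
| 2/5 | 1.72 | 13.8 | 0.92 × 8 = 7.4 |
| 2/6 | 1.83 | 14.6 | not run |
| 5/15 | 2.90 | 23.2 | 1.92 × 8 = 15.4 |

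With independent readings, the fall runs from 2.5 to 8.7 at SD 3 and from 8.5 to 29.0 at SD 10 (1/3 to 5/15 readings).

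**Step 3: effect on the SD.** At SD 8 with independent readings, the noise part of the delta has SD 10.0 (1/3), 8.4 (2/6) and 6.9 (5/15). Required sample size goes with SD squared: (10.0/6.9)² = 2.1. For this component alone, monitoring frequency changes the implied size about twofold. True differences between patients in the size of the fall would dilute that ratio.

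**Step 4: between arms.** With equal reading counts and equal variability, the offset is the same in every arm and cancels. If one arm had 5 post-induction readings and another 15, at SD 5, the arms would differ by 5 × (1.736 − 1.163) = 2.9 units with no effect at all.

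**Step 5: timing of the pre-induction value.** Induction comes at least 30 minutes after the call, so the 5-minute window opens at least 30 − 5 = 25 minutes after drinking ends. Let drinking add s to every reading before induction and t to every reading after. The delta then shifts by s − t and the post-induction minimum by t. A mean-minus-mean delta also shifts by s − t.

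| s | t | Difference in delta (fall) | Difference in lowest post value |
|---|---|---|---|
| 0 | 5 | −5 (smaller fall, benefit seen) | +5 |
| 5 | 5 | 0 | +5 |
| 5 | 3 | +2 (drinking looks worse) | +3 |

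Simulation gave the same differences for the max-min and the mean-based delta.

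**Step 6: what the remedy leaves.** At SD 8, mean-pre minus lowest-post still shows a fall of 6.8 (1/3), 10.1 (2/6) and 13.9 (5/15), because the minimum is itself an extreme. At 2/6 readings the noise SD is 8.4 for max-min, 7.6 with the mean pre-induction reading and 9.5 with the last one. The variance of the minimum of six is about 9.5² − 8² = 26. With an assumed between-patient SD of 15, the unadjusted minimum has SD √(15² + 26) ≈ 16.

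**The case against.** The strongest reply is that little is lost. The benefit named in Section 2.2.2 is on hypotension after induction. If drinking acts only there, the delta shows it in full. The lowest post-induction value is already recorded, and vasopressor dose in the same 15 minutes is a separate outcome. A delta also removes stable differences between patients: about 8 against 16 in SD under the assumptions above. All of this stands, and it is why the delta should be kept.

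Several stronger readings are tempting, and the documents do not support them:

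- A reader might infer that the protocol prescribes highest minus lowest. It does not state a formula; this one follows only from what is recorded.
- A reader might infer that the maximum and minimum cause the cancellation. They do not. Cancellation comes from the timing of the pre-induction value, and a mean-based delta cancels equally.
- A reader might infer that the arm comparison is biased. That needs unequal monitoring or variability between arms, which routine data do not exclude but nothing in the documents shows.
- A reader might infer that recording the highest value hides both dehydration signs. It can hide low pressure, but a heart rate above 90 is exactly what a maximum picks up.

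**Conclusion.** The point holds as a minor one. The delta is undefined. From the recorded values it overstates the absolute fall, by about 7 to 23 units at an assumed within-patient SD of 8 with independent readings and about 3 to 15 with strong serial correlation. It does so by an amount that depends on monitoring frequency. That affects the mean and SD carried into a later power calculation. It does not bias the difference between arms if monitoring is equal.

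Separately, no delta from a pre-induction value taken after the intervention can show a drinking effect common to both periods. Whether drinking acts that way is unknown, so loss of the effect is possible, not certain. It would go too far to infer that the pilot will discard a real target or that the delta should be dropped. SDs, reading counts, correlation and effect sizes are all assumptions. The outcome is exploratory; the primary thirst analysis and n = 174 do not depend on it.

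**What to change.** - In Section 3.5.2, list the lowest post-induction value, reported by arm, as a haemodynamic outcome alongside the delta.
- In Section 3.6.3, record the mean of the readings in the 5 minutes before induction in place of the highest. The last reading is not recommended because it can raise the SD.
- Define the delta explicitly as that mean minus the lowest post-induction value.
- Report the number of readings in each window, by arm.

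The cost is a wording change in two sections and a different pre-induction value taken from data that routine monitoring already produces. A mean is less sensitive than a maximum to a brief high heart rate.

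The limits should be stated. The mean reduces the built-in fall only where there is more than one pre-induction reading, and it does not cure the cancellation; the by-arm post-induction minimum addresses that. The minimum has the larger between-patient SD, still depends on the number of readings, and is affected by vasopressors given in the same 15 minutes. It should therefore supplement the delta and be read together with the vasopressor outcome.
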